### 3.4 Phase 4 – Testing for content validity

To ensure all items in the assessment tool have the content that tests the domain we intend to test, following the pilot the amended test will be presented to the panel of 5 experts in regional anaesthesia, who will be asked to rate the suitability of ultrasound images and questions to performance of the block. This will be on a 4-point Likert scale (1 = definitely not suitable, 2 = probably not suitable, 3 = probably suitable, 4 = definitely suitable).

The content validity of each item will be calculated by dividing the number of experts who rated the item as suitable and very suitable (3 and 4 on the scale) by the total number of experts. Items found to be appropriate by a sufficiently high percentage of participants will be selected. For example, if 26 out of 40 (65%) participants rate an item as suitable or very

suitable then the lower 95% confidence limit for this proportion is 51%, indicating that more than 50% of experts are likely to find it appropriate.

### 3.5 Phase 5 – Psychometric main study testing

The main study assessment tool will be administered to trainees of all levels and consultants, aiming to recruit an equal number across different stages of the RCoA curriculum and of varying regional anaesthesia experience (stage 1; stage 2; stage 3; stage 3 + regional fellowship trained; consultant; consultant with special interest in regional; consultant + regional fellowship trained). Participants will be recruited using emails and flyers sent to schools of anaesthesia across the UK. Each participant will answer a series of demographic questions, including age, gender, handedness, as well as level of training and practical experience in UGRA to account for inconsistencies in clinical exposure at different stages of training.

The exam will consist of constructed response questions (CRQs), which will require the participant to write free-text responses to questions, in line with RCoA examinations. Participants will be provided with sample questions and answers before the test to familiarise themselves with the question format.

The construct validity of the tool will be tested by comparing the scores of anaesthetists with their level of experience specifically in regional anaesthesia. The level of experience is a proxy outcome measure for their proficiency in ultrasound-guided regional anaesthesia. Differences in ultrasound interpretation skills between study groups will be analysed using one-way analysis of variance (ANOVA)/ Rasch modelling. At the end of the assessment, there will be a short questionnaire to allow for participant feedback regarding ease of understanding and suitability of ultrasound images to support the face validity of the test.

The internal reliability of the item responses will be assessed using Cronbach's alpha. An alpha value of 0.70 will be considered sufficient and acceptable for the questions. A split-test method will also be used for each participant to compare the first half of their assessment with the second half to ensure internal consistency of their item responses. The difficulty index calculated for items in the pilot study will be used to ensure a balanced set of test items, in terms of their difficulty, in the first and second halves of the test. All items will be made mandatory. The test will be administered by local investigators via a web-based application. It will have an automatic system of marking to minimise inter-marker differences. It will also be manually checked by investigators who are blinded to the level and identity of the participant. We will aim to recruit a minimum of 250 participants so that there is a stable reliability value, each of whom will be allocated a participant number to pseudonymise the data. The results will be analysed only when recruitment has ended.

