### 3.2 Phase 2 – Content and question generation

A panel of experts in regional anaesthesia will review UGRA nerve blocks and their relevant anatomical structures. The anatomical structures that must be identified on ultrasound for the safe and effective performance of these blocks will be agreed upon using the Delphi method. It will help determine whether these structures are essential for block performance, desirable, expert or not relevant. The experts in the panel will be defined by their experience – they will all be recognised nationally or internationally for their involvement in regional anaesthesia societies and publications. This information will be collated by the Primary and co-investigators to generate a pilot test of UGRA interpretation content and questions.

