### 3.3 Phase 3 – Preliminary testing

The pilot test will be administered by local investigators via a computer-based application (<https://www.classmarker.com/>) to 35-50 trainees and consultants, recruited by email and flyers sent to schools of anaesthesia across the UK. The cohorts will include an equal number of trainees and consultants of varying experience, based on the new RCOA curriculum and the extent of their regional experience (stage 1 (CT1-3); stage 2 (ST4-5); stage 3 (ST6-7); stage 3 + regional fellowship trained; consultant; consultant with special interest in regional; consultant + regional fellowship trained). The pilot test will contain short video clips and images of ultrasound guided regional anaesthesia with questions in a constructed response question (CRQ) format to identify relevant structures, anatomy and clinical knowledge. It is important to recognise that due to the change in the RCoA curriculum, some participants will be familiar with the CRQ format while others might be more familiar with MCQ-based format, or other forms of assessment question. Participants in the pilot and main study will be provided with sample questions and answers prior to the test to familiarise themselves with the question format.

Face validity of the test will also be assessed by asking participants to comment on the ease of understanding and to identify terms that appear ambiguous. Participants will be able to comment in a text box after each item in the questionnaire. They will also be asked to comment on how they would improve the test and any relevant anatomy or clinical

knowledge missing from the questions. The format of the test will be amended based on the comments.

A difficulty index of each item will be calculated by dividing the number of correct responses by the total number of responses, as detailed in Abubakar *et al*'s study, and thus a higher value suggests a question is easier to answer. Any item with a difficulty index of < 50% will be considered too difficult to answer by the respondents and will be considered for removal. This will be compared to the information gathered from the panel of experts on test items, for example whether the anatomical structure is essential, desirable, expert or not relevant to the specific ultrasound guided nerve block.

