# 7. Statistics and Data Analysis

## 7.1 Sample Size Calculation

Sample size for the definitive data capture stage, 'Phase 5 – Psychometric main study testing', will be calculated using a power calculation based on data obtained in the pilot work during 'Phase 3 – Preliminary testing'. For example, internal reliability of the item responses is to be assessed using Cronbach's alpha, an alpha value of 0.70 being considered adequate. With 250 participants completing a 50-item questionnaire it would be possible to show that Cronbach's alpha is significantly higher than 0.6 if the true value is 0.7 i.e. there is

a greater than 85% chance (power) that the 95% confidence interval for Cronbach's alpha will exceed 0.6 and include 0.7.

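### If several questions share a clip, an item-level alpha of 0.70 does not show reliability across clips, and the plan does not say how many questions each clip carries

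*Combined protocol and SAP*

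**What the plan says.** Reliability is part of the primary outcome (sections 2 and 4.1). Section 3.5 sets the unit of analysis, "The internal reliability of the item responses will be assessed using Cronbach's alpha", and the criterion, "An alpha value of 0.70 will be considered sufficient and acceptable for the questions". Section 7.3 repeats the value. Sections 3.5 and 7.3 add a comparison of the first and second halves of the test. The halves are balanced on item difficulty only, and no coefficient or acceptance value is given for the comparison.

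On content, section 3.2 has the experts agree by Delphi "The anatomical structures that must be identified on ultrasound for the safe and effective performance of these blocks", so a block may have several structures. Section 3.3 describes the pilot test as "short video clips and images of ultrasound guided regional anaesthesia with questions in a constructed response question (CRQ) format to identify relevant structures", with anatomy and clinical knowledge also covered. No section says how many questions go with one clip or image, defines what counts as an item, plans a reliability coefficient on clip totals, or plans a check of local dependence.

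The precision example in section 7.1 also works with items. It supposes that 250 people take a test of 50 items, and its target is a finding that "Cronbach's alpha is significantly higher than 0.6 if the true value is 0.7".

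**The concern.** A participant who orients correctly on a clip will tend to answer several of its questions correctly, and one who misreads it will tend to miss several. Those answers then correlate more strongly than answers to questions on different clips. Alpha over items does not distinguish the two sources of correlation. It treats shared success on one clip as evidence of a consistent skill.

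The tool is meant to measure image interpretation in general and to withstand challenge if used for certification (section 1.1). For that purpose the relevant reliability is how well a score would carry over to another set of clips. If clips are shared by several questions, the 0.70 criterion could be met while that reliability is clearly lower.

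**Working it through.** **Inputs from the documents.** N = 250, k = 50 items, alpha 0.6 against a true 0.7, 95% confidence interval, power above 85% (section 7.1); criterion 0.70 (sections 3.5 and 7.3).

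**Assumed, because the documents are silent.** Questions per clip m = 1, 2, 3 or 5; correlation between questions on the same clip r_w = 0.10, 0.15 or 0.20; items of equal variance.

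**1. The plan's own figure.** With (1 − α)/(1 − α̂) distributed as F with N − 1 and (N − 1)(k − 1) degrees of freedom, here 249 and 249 × 49, the upper 97.5% point is 1.185. The lower limit exceeds 0.6 when 1 − α̂ < 0.4/1.185, that is α̂ > 0.663. At a true alpha of 0.7 this has probability 89.4%. Requiring also that the interval include 0.7 removes 2.5 points, giving 86.9%. The event in section 7.1, the "chance (power) that the 95% confidence interval for Cronbach's alpha will exceed 0.6 and include 0.7", is therefore reproduced as above 85%.

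**2. How little correlation 0.70 needs.** From α = k·r/(1 + (k − 1)r), the mean inter-item correlation is r = 0.7/(50 − 0.7 × 49) = 0.7/15.7 = 0.0446. With so low a mean, modest extra correlation within clips can supply much of it.

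**3. Alpha on clip totals when item-level alpha is 0.70.** With J clips of m questions, the between-clip correlation r_b solves (k − 1)r = (m − 1)r_w + (k − m)r_b. A clip total has variance v = m + m(m − 1)r_w, and two clip totals have covariance c = m²r_b. Then clip-level alpha = J·c/(v + (J − 1)c).

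Example with 10 clips of 5 and r_w = 0.15:
- r_b = (49 × 0.0446 − 4 × 0.15)/45 = 0.0352
- v = 5 + 20 × 0.15 = 8
- c = 25 × 0.0352 = 0.880
- alpha = 8.80/(8 + 7.92) = 0.55

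| Questions per clip | Clips | r_w = 0.10 | r_w = 0.15 | r_w = 0.20 |
|---|---|---|---|---|
| 1 | 50 | 0.70 | 0.70 | 0.70 |
| 2 | 25 | 0.68 | 0.67 | 0.65 |
| 3 | 17 | 0.66 | 0.63 | 0.60 |
| 5 | 10 | 0.62 | 0.55 | 0.48 |

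(17 clips of 3 make 51 items; the mean correlation was recomputed for k = 51. In the first row each clip total is a single item, so r_w does not apply.)

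**4. Simulated binary answers.** An extreme case, also assumed: N = 250, 5 clips of 10 questions, ability variance 0.06, clip variance 0.4, unit residual variance, 400 replicates. Mean item-level alpha was 0.74 and reached 0.70 in 90% of replicates. Mean clip-level alpha was 0.32 and never reached 0.70. A split-half coefficient with each clip kept whole in one half averaged 0.31, close to the clip-level value. With two questions per clip, item-level alpha stayed below 0.70 in nearly all replicates of the clustered scenarios.

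**5. Section 7.1 with clips as k.** If the true clip-level alpha is 0.70, the joint event has probability 84.2% with 10 clips and 85.4% with 15. If it is 0.62 with 10 clips, the probability is about 8%.

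**The case against.** The strongest objection is that the deciding fact is missing. The documents list structures per block but do not say that several are asked about from one clip. Pilot items are randomly ordered, timed one by one and rated one by one by the experts, which would fit self-contained items. An item could even be a whole clip with one constructed response, in which case item-level alpha already is clip-level alpha. This stands: the point has to be conditional, and the loss is nil with one question per clip and small with two. A reader might infer that the documents show shared clips, or that the Rasch assumption of local independence is broken. They show neither. They leave the matter open.

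Second, 50 items is only an example, and final length is to be guided by the pilot. That is so, and the table illustrates a range. It does not predict this test.

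Third, the split comparison might expose the problem. It would do so if clips stayed whole within halves. The plan does not require this and sets no acceptance value, so the safeguard is incomplete. Random order does not remove dependence that comes from a shared image. Rasch modelling is named for group differences and construct validity, with no dependence check.

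Fourth, pooling everything that shares a clip or block would mix image interpretation (primary) with anatomical and clinical knowledge (secondary). Competence in a particular block may also be part of what the test should measure. Both objections stand, so the remedy is confined to clips and to the image-interpretation questions.

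**Conclusion.** The point holds conditionally. The plan applies 0.70 to item responses, does not state how many questions share a clip, and has no step that would separate skill across clips from success on a single clip. If several questions share a clip, meeting 0.70 at item level does not establish reliability across clips. For item-level alpha of 0.70 over about 50 items and same-clip correlations of 0.10 to 0.20, the shortfall runs from 0.02 to 0.05 with two questions per clip up to 0.08 to 0.22 with five. Both the number of questions per clip and the correlations are assumptions.

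Two stronger readings are tempting and not supported. One is that the power statement in section 7.1 is wrong; it is right for 50 independent items. The other is that item-level alpha must be dropped as the criterion; nothing in the documents establishes enough clustering to require that, and reporting both coefficients answers the question.

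**What to change.** In section 3.5, state how many questions go with each clip or image and define an item. In sections 3.5 and 7.3:

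- Where questions share a clip or image, compute alpha also on clip totals within the image-interpretation domain, keeping knowledge questions separate. Report it beside item-level alpha, and do not claim reliability across clips on item-level alpha alone.
- Place all questions on a clip in the same half of the split test.
- Check local dependence in the Rasch analysis.

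If clip totals are used, restate section 7.1 with the number of clips as k, and say that the 84.2% (10 clips) or 85.4% (15 clips) applies only if the true clip-level alpha is 0.70.

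No new data or participants are needed for the added analysis, and with one question per clip it reduces to the present plan. The costs are a little more analysis, a constraint on assembling halves that must also balance difficulty, and a reported reliability that may fall below 0.70. The rule for the halves should be fixed before the Phase 5 test is assembled, and the rest before its data are analysed.

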## 4. Study Outcome Measures

### 4.1 Primary Outcome

The primary outcome will be the development of a validated, reliable and defensible assessment tool to test UGRA interpretation skills.

### 4.1 Secondary Outcomes

The secondary outcomes are development a validated, reliable and defensible assessment tool assessing anatomical, clinical knowledge and the performance of ultrasound guided regional anaesthesia:

- Assessment of anatomical knowledge relevant to performing a local anaesthetic injection around peripheral nerves
- Assessment of clinical regional anaesthesia knowledge relevant to performing a local anaesthetic injection around peripheral nerves
  - Assessment of the performance of an ultrasound-guided local anaesthetic injection around peripheral nerve

## 5. Participant Entry

### 5.1 Pre-registration Evaluation

Participants will be required to complete the following tasks to be involved in this research:

- Read a participant information sheet (PIS) about the study.
- Face to face or virtual explanation and consent of the study will be taken by one of the study team members (PI's or co-investigators); written or online consent (digital signature)

### 5.2 Participant Recruitment

Consultant and trainee anaesthetists across the breadth of the curriculum stages, will be invited to participate by email. All potential participants will be given a PIS (approved by a Research Ethics Committee) describing the study on recruitment. The participant will have time to read the PIS and to discuss their participation with study administrators, as required, before providing written consent.

#### 5.3. Inclusion criteria

Any anaesthetic trainee currently registered with the Royal College of Anaesthetists in a UK-training programme and practising consultant anaesthetists who are registered with the General Medical Council.

## 5.4. Exclusion criteria

Staff grade, associate specialist and specialty doctors not enrolled in a UK anaesthetic training programme will be excluded because they encompass a wide range of different experience in regional anaesthesia. Co-investigators, local investigators and pilot test participants will be excluded due to prior experience with the assessment tool.

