### 3. Study Design

This is a prospective, multi-centre study leading to the identification of a validated, reliable and defensible assessment tool for assessing UGRA image interpretation.

Study population	Anaesthetists in the UK
Inclusion	Registered in an approved UK anaesthetic training programme Anaesthetic consultants on the GMC register
Exclusion(s)	Staff grade, associate specialist and specialty doctors not enrolled in a UK anaesthetic training programme
Sample size	Pilot phase: 35-50      Study phase: 250
Duration	12 months
Study centres	Imperial College Healthcare NHS Trust, London  Royal Gwent Hospital, Aneurin Bevan University Health Board, Wales  Southern Health and Social Care Trust, Northern Ireland, UK  Belfast Health and Social Care Trust, Northern Ireland, UK  NHS Greater Glasgow & Clyde, Scotland, UK  Guy's & St Thomas NHS Foundation Trust, London, UK  Frimley Health NHS Foundation Trust, UK
Primary outcome	A validated, reliable and defensible assessment tool to test ultrasound-guided regional anaesthesia image interpretation skills
Secondary outcome(s)	The secondary outcomes are development a validated, reliable and defensible assessment tool assessing anatomical, clinical knowledge and the performance of ultrasound guided regional anaesthesia: 

• Assessment of anatomical knowledge relevant to performing a local anaesthetic injection around peripheral nerves

• Assessment of clinical regional anaesthesia knowledge relevant to performing a local anaesthetic injection around peripheral nerves

• Assessment of the performance of an ultrasound-guided local anaesthetic injection around peripheral nerve

This study will have 5 Phases:

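### The prior-exposure exclusion in Section 5.4 omits the five Phase 4 expert raters, who could sit the Phase 5 test in the groups where high scores count as evidence for the tool

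*Combined protocol and SAP*

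**What the plan says.** Section 5.4 gives exposure to the tool as a reason for exclusion and names three categories of people: "Co-investigators, local investigators and pilot test participants will be excluded due to prior experience with the assessment tool". The exclusion row of the design table in Section 3 covers only "Staff grade, associate specialist and specialty doctors not enrolled in a UK anaesthetic training programme". Section 5.3 admits, besides trainees, "practising consultant anaesthetists who are registered with the General Medical Council". None of these mentions the expert panel.

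The panel's contact with the test is described in two places.

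- **Phase 2 (Section 3.2).** Experts settle the content by a Delphi process: "The anatomical structures that must be identified on ultrasound for the safe and effective performance of these blocks will be agreed upon using the Delphi" […]. Others produce the questions: "This information will be collated by the Primary and co-investigators to generate a pilot test of UGRA interpretation content and questions". Of the experts, the section says that "they will all be recognised nationally or internationally for their involvement in regional anaesthesia societies and publications".
- **Phase 4 (Section 3.4).** After the pilot, "the amended test will be presented to the panel of 5 experts in regional anaesthesia", who rate each item's images and questions for suitability.

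Phase 5 (Section 3.5) aims for equal numbers in seven experience groups. The last two are "consultant with special interest in regional; consultant + regional fellowship trained". Section 1.1 says that construct validity will be shown by higher scores among those with more regional anaesthesia experience. Sections 3.5 and 7.3 name one-way ANOVA/Rasch modelling as the method.

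**The concern.** The plan applies its own reason for exclusion incompletely. Pilot participants are barred because they have met the test. The Phase 4 raters meet a later version, already amended after the pilot and so closer to the one used in Phase 5, and they are not barred.

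The direction of the bias matters more than its size. Prior sight of the items can only help the person who has it, and these people would sit at the experienced end of the scale. A higher score there is what the plan will read as construct validity. Neither Section 3.5 nor Section 7.3 describes any adjustment for exposure. For a tool whose stated aims include defensibility, a validation sample that may contain people who approved its items invites a challenge that is easy to avoid.

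**Working it through.** **The plan's own figure.** The only power statement is in Section 7.1: 250 participants, 50 items, true Cronbach's alpha 0.7 against 0.6, power above 85%. Under Feldt's result, (1 − true alpha)/(1 − estimated alpha) follows an F distribution with 249 and 249 × 49 = 12,201 degrees of freedom. With a two-sided 95% interval:

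- The lower limit exceeds 0.6 with probability P(F > (0.3/0.4) × F₀.₉₇₅) = 89.4%.
- Requiring the interval also to include 0.7 removes 2.5 points, leaving 86.9%.

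The stated figure reproduces. It concerns reliability and is not in dispute here. The plan gives no significance level or effect size for the construct-validity comparison.

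**Inputs for the bias**

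- Group size: 250/7 = 35.7, about 36 (Section 3.5; equal groups assumed).
- Exposed raters: m = 5 (Section 3.4).
- Score gain from prior sight, d: not in the documents. Assumed range 0.5 to 2 SD.
- ANOVA significance level: not in the documents. Assumed 5%.

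**Shift in a group mean.** Shift = (m / group size) × d.

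| Assumed gain d | All 5 in one group: 5/35.7 × d | Spread over the three consultant groups: 5/107.1 × d |
|---|---|---|
| 0.5 SD | 0.07 SD | 0.02 SD |
| 1 SD | 0.14 SD | 0.05 SD |
| 2 SD | 0.28 SD | 0.09 SD |

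**Effect on the ANOVA.** Seven groups of 36 were simulated with 40,000 replicates per scenario. Five members of the top group were raised by d.

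| Assumed gain d | Rejection rate, no true difference | Rejection rate, assumed true trend of 0.1 SD per group |
|---|---|---|
| none | 5% | 64% |
| 0.5 SD | 5.5% | 71% |
| 1 SD | 6.9% | 78% |
| 2 SD | 13.5% | 89% |

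In the last column a true difference exists, so rejecting is correct. What is distorted there is the strength of the evidence. At a 1 SD gain the mean difference between the top and bottom groups rises from 0.60 to 0.74 SD.

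**After the correction.** Excluding the five raters removes 5/250 = 2% of candidates and takes the shift to zero. If they are replaced, N stays at 250 and the 86.9% stands.

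**The case against.** **The panellists may already be excluded.** If all five are co-investigators, Section 5.4 covers them. The research-team list that Section 9 points to was not available for this check, so this cannot be ruled out. But Section 3.2 gives the panel and the co-investigators separate roles, and nothing says that they are the same people. The documents also do not say whether every panellist is based in the UK or would wish to enrol. These points make the bias conditional; they do not close the gap in the rule.

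**A large gain may be implausible.** Nationally recognised experts may already score near the ceiling, the more so because items with a difficulty index below 50% are candidates for removal (Section 3.3) or are excluded (Section 7.3). This stands as a reason to lean towards the lower end of the assumed range.

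**Stronger readings that the documents do not support:**

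- *The experts wrote the test.* Section 3.2 has them agree on structures. The Primary and co-investigators generate the questions, and co-investigators are already excluded.
- *Everyone on the Phase 1 and 2 panels is compromised.* Those panels review guidelines, list relevant knowledge and classify structures. They are not said to see items. Knowing which structures were chosen is a weaker exposure than seeing the questions.
- *Many more than five are exposed.* Section 3.4 uses 26 of 40 raters in an illustration of a confidence limit, but it states a panel of five. The size of the Delphi panel is not given, so a larger count would be invented.
- *The error rate reaches about 9% at a 1 SD gain.* That is a pairwise test: 0.139 SD against a standard error of √(2/36) = 0.236 SD gives 9.1%. The plan names an analysis across all groups, for which the figure is 6.9%.
- *Raters must also be kept out of the pilot.* The Phase 4 rating follows the pilot, and pilot participants are already barred from the main study.

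**Conclusion.** The point holds as an incomplete exclusion rule. Followed as written, Section 5.4 would let up to five people who have rated the amended test sit it in Phase 5, most likely in high-experience consultant groups, and any bias would favour the tool.

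The size is small to modest. At an assumed 1 SD gain, with all five in one group, the ANOVA's false rejection rate rises by about two percentage points, and less if they are spread over several groups. The figures rest on five raters enrolling, none of them already excluded, equal groups of about 36, a 5% test and an exposure gain that the documents do not give. A top group that recruits below its share would dilute the five less. The case for acting is the one-directional bias and the very low cost of removing it; the documents do not show that the validation would fail without the change.

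**What to change.** Add one sentence to Section 5.4 and to the exclusion row of the design table in Section 3: *Members of the Phase 4 expert panel, and any other panel member who has seen test items, will be excluded from Phase 5 because they have already been exposed to the test.*

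The second clause covers any Phase 1 or 2 panellist who did see items, without barring those who did not. No change to Phase 3 eligibility is needed.

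The cost is at most about five eligible consultants, 2% of 250. They can be replaced from the same recruitment, so neither the target sample size nor the power stated in Section 7.1 changes.
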